2.4 Secondary Endpoints

We will analyze differences in respiratory rate, tidal volume, arterial blood pressure, heart rate, global duration of mechanical ventilation and intravenous remifentanil infusion, length of stay in ICU and in hospital.

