4.3.1 Visits

Visits will be performed at the baseline and every 4 hours for the first 24 hours, every 6 hours for day 2 and day 3.

At each visit we will record:

- An Arterial Blood Gases (ABG) sample will be collected and ABG parameters recorded (pH, PaCO₂, PaO₂, HCO₃⁻, Lactates, SaO₂);
- Glasgow Coma Scale, RASS (see APPENDIX 1-2), the dosage of remifentanil and TTS-fentanyl;
- Respiratory parameters: Ventilation mode, Pressure Support, Respiratory Rate (RR), Tidal Volume(V_t), peep, FiO₂, EtCO₂, SpO₂; if patient is spontaneously breathing: FiO₂, RR, SpO₂.
- Hemodynamic parameters (Heart Rate, SBP/DBP/MAP, need for vasopressors, inotropes).

A baseline 1-hour recording of EAdi, flow, and Paw waveforms will be performed, as well as after 1, 6, 12, 24 for the first day from the time of randomization and every 24 hours for the following days until the end of the observation period for the primary endpoint. Each recording will last one hour for patients mechanically ventilated, 10 minutes for patients weaned from the mechanical ventilator.

Four different situations are possible:

- For patients connected to the mechanical ventilator in pressure support ventilation (PSV), we will perform an expiratory pause maneuver and an inspiratory pause maneuver (both lasting enough to have 2 or 3 spontaneous breaths) with an interval of one minute between each maneuver. The maneuvers will be performed after 30 and 60 minutes from the start of recording.
- If in the meantime the patient is weaned from the mechanical ventilator and spontaneously breathing through a tracheostomy, we will temporarily reconnect the patient to the mechanical ventilator, in PSV mode, with zero peep (ZEEP), we will perform an expiratory

pause maneuver and an inspiratory pause maneuver (both lasting enough to have 2 or 3 spontaneous breaths) with an interval of one minute between each maneuver. In these weaned patients, the maneuvers will be performed after 5 and 10 minutes from the start of recording that will last only 10 minutes;

- If in the meantime the patient is weaned from the mechanical ventilator, extubated, spontaneously breathing and able to cooperate, the patient will be asked to inspire in a close system connected to a pneumotachograph to estimate P_{aw} . The maneuver will be performed after 5 and 10 minutes from the start of recording that will last only 10 minutes;

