- If in the meantime, the patient is weaned from the mechanical ventilator, extubated, spontaneously breathing, and unable to cooperate we will use as a surrogate the neuromechanical efficiency calculated when the patient was connected to the ventilator. The recording will last only 10 minutes.

We will calculate $PEI_{occl,paw}$, the $Pmus_{EAdi}$ waveform, and the two most validated indexes of inspiratory effort: $\Delta Pmus$ and the PTP_{EAdi} (a good indicator of the metabolic work of breathing). We will analyze the dynamic transpulmonary driving pressure, corresponding to the sum of the pressure support level and $Pmus_{dyn}$, and representing a surrogate of dynamic stress that takes into account the chest wall elastance. Moreover we will measure the plateau pressure, the positive end-expiratory pressure (PEEP), and we will calculate the driving pressure and the static compliance of the respiratory system.

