4.6 End of Study (EOS) visit (individual subject)

This visit occurs at the discharge from the intensive care unit or in case of death after the observation period for the primary endpoint and is defined as the last visit performed by an individual subject for the study. This visit may occur earlier for subjects who prematurely withdraw from the study.

In this visit we will record:

- An Arterial Blood Gases (ABG) sample will be collected and ABG parameters recorded (pH, PaCO₂, PaO₂, HCO₃⁻, Lactates, SaO₂);
- Glasgow Coma Scale, RASS;
- Respiratory parameters: Ventilation mode, Pressure Support, Respiratory Rate, Tidal Volume, peep, FiO₂, EtCO₂; if patient is spontaneously breathing: FiO₂, RR, SpO₂;
- Hemodynamic parameters (Heart Rate, SBP/DBP/MAP);
- Data on the global duration of opioid therapy/length of stay (LOS) in hospital and ICU.

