Analysis of the primary efficacy criterion (AUC of the work of breathing) and other quantitative variables will be assessed with the Wilcoxon-Mann-Whitney sum of rank test. Categorical outcomes will be compared with the chi-square test, or Fisher's exact test, as appropriate: Cochran-Mantel-Haenszel statistics will be reported for all these results. Two-way analysis of variance (ANOVA) for repeated measures with Bonferroni correction will be used to determine the differences in work of breathing per breath, inspiratory effort, delta EAdi, plateau pressure, P 0.1 respiratory rate, tidal volume, arterial blood pressure, heart rate in the two groups. Comparisons between groups regarding these variables at each study time point will be performed with the Student's t-test or Mann-Whitney test, as appropriate. Mean difference and 95% confidence interval [CI95%] are reported for most significant results.

Two-tail p values≤0.05 Will be considered significant. Statistical analysis will be performed with SPSS software package (SPSS Inc. Released 2009. PASW Statistics for Windows, Version 18.0. Chicago: SPSS Inc.).

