6.1 Sample size calculation

As said previously, the primary endpoint is to demonstrate that the area under the curve (AUC) of the work of breathing per minute (assessed at 1, 6, 12, 24, 48, and 72 hours) in the intervention group is not higher than the control group. Data on the work of breathing of ICU patients undergoing mechanical ventilation while on remifentanil continuous infusion are lacking. However, there are studies suggesting that a sample of 10 patients is adequate to draw significant conclusions on the physiological endpoints related to respiratory mechanics and work of breathing among patients with respiratory failure (Delorme et al. 2017; Lellouche et al. 2002; Prat et al. 2003; LHer et al. 2005). Thus, for this phase II, pilot, randomized trial, using a conservative approach and considering an attrition rate lower than 10%, we planned to enroll 12 patients per group, for a total sample of 24 patients in 12 months. Julius et al., in their study published on pharmaceutical statistics in 2005 confirmed that a minimum 12 subjects per group are enough for a pilot randomized trial (Julious et al. 2005).

7. Premature withdrawal from the study

Subjects may voluntarily withdraw from the study without justification for any reason at any time. Subjects are considered withdrawn if they state an intention to withdraw further participation in all components of the study (i.e., withdrawal of consent), die within the observation period for the primary endpoint, or are lost to follow up. If a subject withdraws consent, no further data will be collected in the CRF from the date of withdrawal onward. The investigator may withdraw a subject from the study (without regard to the subject's consent) if he/she believes that continued participation in the study would be contrary to the best interests of the subject.

The reason for premature withdrawal from the study must be recorded in the CRF.

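### Durations and stays are ranked without a rule for death, so an early death can count as a short, favourable value; and the repeated-measures ANOVA can lose weaned patients for tidal volume

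*Combined protocol and SAP*

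**What the plan says.** **Durations and stays.** Section 2.4 lists as secondary endpoints "global duration of mechanical ventilation and intravenous remifentanil infusion, length of stay in ICU and in hospital". Section 6 names a separate set of variables for repeated-measures ANOVA, and these durations are not among them. They therefore fall under its general sentence, by which the "primary efficacy criterion (AUC of the work of breathing) and other quantitative variables will be assessed with the Wilcoxon-Mann-Whitney sum of rank test". The Abstract assigns the ANOVA to secondary endpoints in general, but one duration per patient cannot enter a repeated-measures analysis, so the reading from section 6 stands.

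**Death.** Section 4.6 places the End of Study visit at ICU discharge or "in case of death after the observation period for the primary endpoint". Among the items taken there is "Data on the global duration of opioid therapy/length of stay (LOS) in hospital and ICU". Ventilation duration is not on that list. Section 7 classes as withdrawn those who "die within the observation period for the primary endpoint, or are lost to follow up". No section says how a death, early or late, enters the duration tests.

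**Repeated measurements.** Section 6 puts tidal volume on the repeated-measures ANOVA list and adds group comparisons at each time point. Section 4.3.1 lists tidal volume at visits, but for a spontaneously breathing patient it names only inspired oxygen fraction, respiratory rate and oxygen saturation. It also foresees weaning inside the 72-hour window. No imputation or mixed model is mentioned.

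**The concern.** A rank test on durations treats a small number as a good result. A patient who dies in the ICU on day 5 has a closed stay of 5 days and, without a rule, can rank ahead of a survivor discharged on day 20. Sections 1.4 and 9 name shorter ventilation as a hoped-for benefit, and section 9 adds shorter ICU stay. An arm with more early deaths could therefore look better on the endpoints that would be used to argue for a larger trial. With 12 per arm, two deaths are a sixth of an arm.

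For tidal volume, classical repeated-measures ANOVA uses only patients with every time point. If weaned patients lack later values, the comparison moves towards those still ventilated. That subset is formed after randomisation by an outcome the treatment is meant to change.

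**Working it through.** **1. The plan's own figure.** Section 6.1 takes 10 patients by precedent and attrition below 10%: 10 / 0.90 = 11.1, rounded up to 12 per group, 24 in total. This reproduces. There is no power calculation, and no mortality or weaning rate is given, so every count of deaths or weaned patients below is an assumption.

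**2. Null behaviour of the test.** For 12 v 12, the null SD of the Mann-Whitney U is sqrt(12 × 12 × 25 / 12) = 17.32. The exact two-sided 0.05 test rejects at U ≤ 37, which has probability 2.2% in each direction.

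**3. Excess deaths in one arm, no true effect.** Let k of 12 patients in one arm be excess deaths at mean quantile q of the duration distribution. The chance that a patient in that arm has the shorter duration is

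P = (k/12)(1 − q) + ((12 − k)/12)(0.5).

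| Excess deaths k | Ranked shortest (q = 0): P | Shift in U, in null SD | False shorter result | Lower half (q = 0.25): P | False shorter result |
|---|---|---|---|---|---|
| 0 | 0.50 | 0 | 2.2% | 0.50 | 2.2% |
| 1 | 0.542 | 6/17.32 = 0.35 | 4.0% | 0.521 | 3.2% |
| 2 | 0.583 | 12/17.32 = 0.69 | 7.1% | 0.542 | 4.4% |
| 3 | 0.625 | 18/17.32 = 1.04 | 12.4% | 0.563 | 6.1% |

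The rates come from 200,000 simulated trials; a fresh simulation agreed to about 0.1 percentage point. At q = 0.5 the formula gives P = 0.50 for any k, so there is no shift.

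**4. Random mortality.** Assume log-normal ICU stays (median about 23 days, log-SD 0.6), deaths on days 3 to 14 and no effect on stay. At 20% mortality in both arms the plain test falsely favours group 2 in 2.2% of trials. At 10% v 30% (more deaths in group 2) it does so in 10.4%. With deaths ranked worst that becomes 0.2%, and the test favours group 1 in 12.0%, which reflects the mortality difference.

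**5. Tidal volume.** Table 1 gives a baseline and 14 visits, so 15 possible values. A patient weaned between 42 h and 48 h has given baseline, 4, 8, 12, 16, 20, 24, 30, 36 and 42 h: 10 of 15. If all visits enter the ANOVA, this patient contributes none of them. Section 6 does not name the time points, so 10 of 15 is illustrative. Losing 2 or 3 of 12 per arm at random widens a confidence interval by sqrt(12/10) = 1.095 or sqrt(12/9) = 1.155, about 10 to 15%.

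**6. Bias, under assumptions.** In a 300-trial simulation with a true difference of 0.80, where a higher last value made weaning likelier, complete rows averaged 7.1 and 4.8 of 12 per arm. They estimated 0.59, against 0.79 from a mixed model. With no true difference, both methods were close to zero. A false difference under the null needs unequal, value-related weaning: with 3 v 1 weaned, taken from the highest values, complete rows gave −0.22 patient SD and the mixed model 0.02.

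**The case against.** **Size.** The inflation needs unequal mortality. Section 6.1 expects attrition below 10%, about one patient per arm (12 × 0.10 = 1.2). If mortality were 10% in each arm, an excess of three or more deaths in a given arm would have probability of about 4%. Patients enter late in their ICU course; if durations count from admission or intubation, a death need not rank shortest. All of this stands and limits the size. It does not supply the missing rule.

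**Cost of worst rank.** Assume a real benefit (log-scale shift 0.9, SD 0.7) and equal mortality. Power falls from 69% to 39% at 20% mortality, and from 75% to 59% at 10%. The plain-test figures depend on where deaths fall: if equal numbers all ranked shortest, the plain test would by symmetry lose about as much. The cost is real and must be stated. Worst rank should also not overwrite a duration completed before a later ward death.

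**ANOVA.** The time-point tests use available values. Flow is recorded at 24, 48 and 72 h, and weaned tracheostomised patients are reconnected for recordings, so some tidal volumes may be recoverable. Respiratory rate, haemodynamics and EAdi measures continue after weaning. This reduces the loss without removing it.

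**A stronger reading that does not hold.** A reader might infer that deaths or weaning also distort the primary AUC. No section states a raw AUC cut off at death, and section 7 classes deaths within 72 h as withdrawn. Weaned patients continue to be recorded on the "following days until the end of the observation period for the primary endpoint", each by a set method. Even for an extubated patient who cannot cooperate, "we will use as a surrogate the neuromechanical efficiency calculated when the patient was connected to the ventilator" is the stated rule. Nor would averaging over observed hours be a safe change. Section 1.2 puts the full patch effect at 12 to 24 h, so an average built on early recordings could dilute a difference towards non-inferiority.

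**Conclusion.** The point holds for two stated methods. First, the plain Wilcoxon test of durations and stays lets an early ICU death rank as favourable. For opioid duration and stay this follows from section 4.6; for ventilation duration it is an inference. For deaths within 72 h the plan leaves open whether they enter these tests at all. The false rate of a significantly shorter duration rises from 2.2% to between 3.2% and 12.4% for one to three excess deaths in one arm, depending on where they rank. It does not rise with equal mortality or if the deaths fall on average at the median. Second, a patient weaned within 72 h can leave the tidal-volume ANOVA with all earlier values. The bias there depends on value-related weaning, which the documents cannot settle.

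The severity is minor to moderate: these are secondary endpoints of a 24-patient pilot, but the plan tests them at 0.05 and the remedy is cheap. The primary AUC is not part of this conclusion.

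**What to change.** 1. **Durations and stays.** Keep the Wilcoxon test. Give the worst tied rank to any patient who dies before the duration in question is completed: before liberation from the ventilator, end of remifentanil, ICU discharge or hospital discharge respectively. Include deaths within 72 h. A patient who completed a duration and died later keeps that value. Report deaths by arm, and the plain analysis as sensitivity. State that worst rank mixes mortality with duration and loses power when deaths are unrelated to treatment.

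2. **Repeated measurements.** Replace the repeated-measures ANOVA by a linear mixed model with arm, visit, arm by visit, baseline value and a random patient effect, using all available values. The main gain is for tidal volume and other ventilator-derived variables. State that the model assumes data missing at random and in effect estimates values as if the patient were still ventilated.

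3. **Primary AUC.** No change is proposed here.

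**Cost.** A few sentences in section 6, a few hours of analysis and no extra patients. Section 4.3.2 already records death and follows patients to hospital discharge. However, the End of Study visit falls at ICU discharge and no data items are named for the ward period, so the case report form should be checked for hospital discharge date and vital status.

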6.1 Sample size calculation

As said previously, the primary endpoint is to demonstrate that the area under the curve (AUC) of the work of breathing per minute (assessed at 1, 6, 12, 24, 48, and 72 hours) in the intervention group is not higher than the control group. Data on the work of breathing of ICU patients undergoing mechanical ventilation while on remifentanil continuous infusion are lacking. However, there are studies suggesting that a sample of 10 patients is adequate to draw significant conclusions on the physiological endpoints related to respiratory mechanics and work of breathing among patients with respiratory failure (Delorme et al. 2017; Lellouche et al. 2002; Prat et al. 2003; LHer et al. 2005). Thus, for this phase II, pilot, randomized trial, using a conservative approach and considering an attrition rate lower than 10%, we planned to enroll 12 patients per group, for a total sample of 24 patients in 12 months. Julius et al., in their study published on pharmaceutical statistics in 2005 confirmed that a minimum 12 subjects per group are enough for a pilot randomized trial (Julious et al. 2005).

7. Premature withdrawal from the study

Subjects may voluntarily withdraw from the study without justification for any reason at any time. Subjects are considered withdrawn if they state an intention to withdraw further participation in all components of the study (i.e., withdrawal of consent), die within the observation period for the primary endpoint, or are lost to follow up. If a subject withdraws consent, no further data will be collected in the CRF from the date of withdrawal onward. The investigator may withdraw a subject from the study (without regard to the subject's consent) if he/she believes that continued participation in the study would be contrary to the best interests of the subject.

The reason for premature withdrawal from the study must be recorded in the CRF.

7.1 Premature termination or suspension of the study

The Sponsor has the right to close the study (or, if applicable, individual segments (e.g. treatment arms; dose steps; centers)) at any time, which may be due, but not limited to, the following reasons:

- If risk-benefit ratio becomes unacceptable owing to, for example: Safety findings from this study (e.g. SAEs)
- If the study conduct (recruitment rate; drop-out rate; data quality; protocol compliance) does not suggest a proper completion of the trial within a reasonable time frame and a proper quality status.

7.2 Medical care of subjects after withdrawal from the study

After the subject's study completion or premature withdrawal from the study, whichever applies, the investigator/delegate will explain to subjects what treatment(s)/medical care is necessary and available according to local regulations. Such care may include the use of drugs that were forbidden during concomitant study treatment administration.

8. Safety definitions and reporting requirements

8.1 Safety definitions

8.1.1 Definition of adverse events

An AE is any untoward medical occurrence, i.e., any unfavorable and unintended sign, including an abnormal laboratory finding, symptom, or disease that occurs in a subject during the study, whether or not considered by the investigator as related to the study treatment.

AEs include

- Exacerbation of a pre-existing disease if considered medically relevant;
- Increase in frequency or intensity of a pre-existing episodic disease or medical condition;
- Disease or medical condition detected or diagnosed during the study even though it may have been present before the start of the study;
- Continuous persistent disease or symptoms present at study start that worsen following the signing of the informed consent form;
- Laboratory test abnormalities if they represent a clinically significant finding (symptomatic or not), which was not present at study start or worsened during the course of the study as per investigator's judgment, or led to interruption or permanent discontinuation of study treatment.

8.1.2 Definition of adverse drug reaction (ADR)

Considering the new usage that is proposed in this study for TTS-fentanyl and that the therapeutic dose is not well established, all noxious and unintended responses to TTS-fentanyl related to any dose should be considered adverse drug reactions.

8.1.3 Definition of serious adverse events

An SAE is defined by the ICH guidelines as any AE fulfilling at least 1 of the following criteria:

- Fatal;
- Life-threatening: refers to an event in which the subject was at risk of death at the time of the event. It does not refer to an event that hypothetically might have caused death had it been more severe;
- Requiring prolongation of hospitalization;
- Resulting in persistent or significant disability or incapacity;
- Congenital anomaly or birth defect;
- Medically significant: refers to important medical events that may not immediately result in death, be life-threatening, or require hospitalization but may be considered medically significant based upon appropriate medical judgment, as they may jeopardize the subject, and/or may require medical or surgical intervention to prevent one of the outcomes listed in the definition above.

8.2 Reporting of adverse events

All AEs with an onset date and time from study drug initiation up to 24 hours after study treatment discontinuation (i.e., the 24-hour safety follow-up period) must be recorded on specific AE forms of the CRF. Those AEs occurring from the signature of the informed consent form until End of Study will also be recorded on an AE form in the CRF if they are believed to be related to a protocol-mandated procedure.

Information to be collected in an AE form in the CRF includes date and time of onset, action taken with the study treatment, outcome of AE, date of resolution (if applicable) and PI's assessment of seriousness and intensity, and relationship to study treatment, study design or protocol mandated procedures. For AEs related to cardiac rhythm abnormalities, additional ECG parameters may be collected.

If the intensity of an AE worsens during study treatment administration, only the worst intensity should be reported on the AE form. If the AE lessens in intensity, no change in the severity is required to be reported.

For AEs ongoing at the start of study treatment, the worsening of the AE after the start of study treatment will be recorded as a separate AE with the new intensity.

Follow-up information on any ongoing AEs obtained after the subject's EOS visit will not be collected in the CRF.

9. Risk-Benefit Assessment

In an ICU setting, in which patients are continuously monitored 24 hours a day and mechanically ventilated, it can be stated that the risks related to the use of TTS-fentanyl are few. There is obviously a consistent risk of developing an opioid addiction, already present using remifentanil, that compared to fentanyl is stronger and short-acting. Respiratory depression is easily and early detected. On the other hand, an alternative and "needle-free" route of administration of an opioid,

fentanyl, that is different from a pharmacokinetic point of view if compared to remifentanil, could help in IV opioids weaning, it can reduce the length of mechanical ventilation, and length of stay in ICU, decreasing the risks related to the stay in an ICU setting as infections rate and increases in costs. Moreover, TTS-fentanyl could theoretically be exported out from the ICU to the medical wards, allowing more gradual and physiological weaning from opioids.

10. Data handling

The investigator is responsible for ensuring the accuracy, completeness, and timely reporting of subject data. All source documents should be completed in a neat, legible manner to ensure accurate interpretation and traceability of the data. Data reported in the CRF derived from source documents must be consistent with the source documents.

The investigator must ensure that data confidentiality is maintained. On CRF or other documents, subjects must be identified only by a number and never by their name or initials, date of birth, hospital numbers, or any other personal identifier. The investigator must keep a subject identification code list at the site, showing the subject number, the subject's name, date of birth, and address or any other accepted identifiers. Documents identifying the subjects (e.g., signed informed consents) must be kept in strict confidence by the investigator.

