4.2 Treatment Period

The treatment period starts immediately with the baseline assessments.

In Group 1, in which remifentanil infusion is administered alone, the infusion rate will be increased or decreased according to the study protocol based on PaCO₂ value resulting from the Arterial Blood Gases sample (ABG) collected at each visit.

In Group 2, TTS-fentanyl will be administered with a starting dose of 50 mcg/hr simultaneously with the preexistent remifentanil continue infusion. Remifentanil infusion rate will be increased or decreased based on PaCO₂ value resulting from the Arterial Blood Gases sample (ABG) collected at each visit. After randomization, the TTS-fentanyl dose can be modified every 24 hours according to the study protocol to achieve the desired effect in terms of PaCO₂ value resulting from the Arterial Blood Gases sample (ABG) collected.

A priori we will no exceed 0,2 mcg/kg/min for remifentanil infusion in both arms.

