4.4 Observation period for the primary endpoint

This period covers the interval over which the subject may qualify for the primary endpoint of the study. It starts with the randomization and ends 72 hours after randomization. After this period the treatment duration will be dependent on the subject's clinical course and the investigator's judgment on the perceived need to continue the study drug. The use of TTS-fentanyl will not be allowed in remifentanil alone group even after the end of the observation period for the primary outcome.

4.5 24-hour safety follow-up period

This period starts with the permanent discontinuation of the study drug (TTS-fentanyl) and ends 24 hours later. Subjects must not be discharged from the hospital until the end of this period.

New Adverse Events occurring in this period are recorded in the case report form (CRF).

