36 hours* (visit 8)	ABG sample, respiratory and hemodynamic parameters, GCS, RASS, dosage of remifentanil and TTS-fentanyl
42 hours* (visit 9)	ABG sample, respiratory and hemodynamic parameters, GCS, RASS, dosage of remifentanil and TTS-fentanyl
48 hours* (visit 10)	ABG sample, respiratory and hemodynamic parameters, GCS, RASS, dosage of remifentanil and TTS-fentanyl, Recording of EAdi, flow, and Paw
54 hours* (visit 11)	ABG sample, respiratory and hemodynamic parameters, GCS, RASS, dosage of remifentanil and TTS-fentanyl
60 hours* (visit 12)	ABG sample, respiratory and hemodynamic parameters, GCS, RASS, dosage of remifentanil and TTS-fentanyl
66 hours* (visit 13)	ABG sample, respiratory and hemodynamic parameters, GCS, RASS, dosage of remifentanil and TTS-fentanyl
72 hours* (visit 14)	ABG sample, respiratory and hemodynamic parameters, GCS, RASS, dosage of remifentanil and TTS-fentanyl, Recording of EAdi, flow, and Paw
End of observation period for the primary endpoint	72 hours after randomization

Treatment suspended	The treatment duration will be dependent on the subject's clinical course and the investigator's judgment on the perceived need to continue the study drug
Safety FU period	Permanent discontinuation of TTS-fentanyl: start of 24 hours of Safety Follow up Period (any adverse event will be recorded on the CRF)
End of Study Visit	This visit occurs at the discharge from the ICU or in case of death after the observation period for the primary endpoint ABG sample, respiratory and hemodynamic parameters, GCS, RASS, Data on the global duration of opioid therapy/length of stay (LOS) in hospital and ICU

*Hours from randomization

Table 1. Study visits and assessments

6. Statistical analysis

Distribution normality will be assessed with the Kolmogorov-Smirnov test. Continuous variables will be reported expressed as medians (interquartile ranges). Qualitative variables will be reported as frequencies.

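### The end of general adverse-event recording is undefined or ambiguous in Group 1, so the two arms' recording windows are not the same

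*Combined protocol and SAP*

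**What the plan says.** Section 8.2 has two recording rules.

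- **General AEs:** the form takes "All AEs with an onset date and time from study drug initiation up to 24 hours after study treatment discontinuation". A parenthesis in the same sentence identifies the closing 24 hours with the safety follow-up period.
- **AEs from consent to End of Study:** these are also recorded, but only "if they are believed to be related to a protocol-mandated procedure".

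Section 4.5 defines the safety follow-up: "This period starts with the permanent discontinuation of the study drug (TTS-fentanyl) and ends 24 hours later". Table 1 agrees: "Permanent discontinuation of TTS-fentanyl: start of 24 hours of Safety Follow up Period". Section 5.3 also identifies the study drug as TTS-fentanyl.

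Section 4.4 keeps that drug out of the control arm: "The use of TTS-fentanyl will not be allowed in remifentanil alone group even after the end of the observation period". After 72 h, continuation rests on the investigator's "judgment on the perceived need to continue the study drug".

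On the start of recording, 8.2 also uses a broader term ("For AEs ongoing at the start of study treatment"), and 4.2 describes a treatment period covering both groups: "The treatment period starts immediately with the baseline assessments".

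**The concern.** A by-arm AE count can be read as a comparison of event rates only if both arms are recorded over the same time. Here the general AE window closes on an event, removal of the last patch, that cannot happen in Group 1. Whoever completes the forms must improvise an end for 12 of the 24 patients. In Group 2 the end moves with a treatment decision taken after randomisation.

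What is at stake is any tabulation of general AEs and non-fatal SAEs by arm. Its use matters because 7.1 names safety findings, including SAEs, among the reasons for closing the study, and 8.1.2 describes a new usage whose therapeutic dose is not well established. To judge whether the patch adds harm, a control rate recorded over the same period is needed.

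**Working it through.** The plan gives no figure to reproduce. The check sets the window's anchors side by side, then illustrates the size.

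**1. Start.** Read literally, initiation of the study drug gives Group 1 no start. But 8.2 also refers to the start of study treatment, and 4.2 supplies a treatment period for both groups. A workable start exists.

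**2. End, literal reading.** 8.2 → safety follow-up → 4.5 and Table 1 → permanent discontinuation of TTS-fentanyl. Group 2 ends at last patch plus 24 h. Group 1 has no such event (4.4), and no other section supplies a substitute.

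**3. End, alternative reading.** Take study treatment as the assigned treatment. Group 1 then ends 24 h after remifentanil stops. Three problems remain:
- It contradicts the parenthesis in 8.2, because 4.5 mentions only TTS-fentanyl.
- Group 2 receives both drugs (4.2), so its own end becomes unclear.
- Duration of the remifentanil infusion is a secondary endpoint (2.4), so the length of safety recording would depend on an outcome.

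**4. Other provisions.** The consent-to-End-of-Study rule is the same in both arms but limited to procedure-related AEs. Section 4.3.2 records reintubation, infection, death and tracheostomy regardless of arm. The common visits (4.3.1, Table 1) give blood-gas and haemodynamic data to 72 h in both arms. None of these covers general AEs.

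**5. Illustration.** Inputs from the documents: 72 h observation period (4.4), 24 h follow-up (4.5), 12 patients per group (6.1). Assumptions:
- Group 1 recording is improvised to stop at 72 h.
- Group 2 starts the patch at randomisation and wears it for exactly 72 h, so its window is 72 + 24 = 96 h.
- The AE rate r is constant and identical in both arms, 0.1 per patient-day, range 0.05 to 0.2. The documents give no AE rate.

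P(at least one AE) = 1 − exp(−r × days).

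| r per day | Group 1, 3 days | Group 2, 4 days |
|---|---|---|
| 0.05 | 1 − exp(−0.15) = 13.9% | 1 − exp(−0.20) = 18.1% |
| 0.1 | 1 − exp(−0.30) = 25.9% | 1 − exp(−0.40) = 33.0% |
| 0.2 | 1 − exp(−0.60) = 45.1% | 1 − exp(−0.80) = 55.1% |

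Expected events at r = 0.1: 12 × 3 × 0.1 = 3.6 versus 12 × 4 × 0.1 = 4.8. The ratio of expected events, 4/3 = 1.33, does not depend on r. With one common 96 h window both arms give 33.0% and 4.8 events.

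**The case against.** The best defence is that 8.2 ends at discontinuation of study treatment. If that term is good enough to give Group 1 a start, it should also give it an end, 24 h after remifentanil stops, and the duration of opioid therapy is collected (4.6). In a single-centre trial one team could apply one rule throughout. This stands in part: it makes the end ambiguous rather than plainly absent. It does not remove the conflict with 4.5, and it does not equalise the windows.

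The second defence is that the consequence is small. Section 6 names no specific AE test, and 7.1 is a sponsor judgement with no threshold on arm counts. Most of the 2.5 safety endpoints are recorded the same way in both arms. (Neuromuscular blockade and intracranial pressure have no scheduled visit item in either arm, which is a separate matter.) All of this stands and limits the point to by-arm AE tabulation and its use in the risk-benefit judgement.

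The third is that the patch anchor has a purpose. It covers patch-related reactions (8.1.2) and holds patients in hospital for 24 h after the patch stops (4.5). That is a good reason to keep it for Group 2, but it does not make it suitable as the end of recording for both arms.

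A reader might go further and infer that Group 1 would have no safety data, or that counts must be biased against fentanyl. The documents support neither. Several events are recorded regardless of arm, and the direction depends on treatment durations that the documents do not give. Nor does 8.1.1 contradict 8.2: one defines an AE, the other says which are recorded.

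**Conclusion.** The point holds in this form: the end of general AE recording in Group 1 is undefined on the literal text and ambiguous on the most generous reading. Either way the windows are tied to treatment duration after randomisation and are not common to the arms.

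On durations built from the protocol's own 72 h and 24 h, the mismatch alone gives 26% (14 to 45%) versus 33% (18 to 55%) of patients with at least one AE, or 3.6 versus 4.8 events, with identical true rates. The percentages rest on the assumed rate and on the improvised 72 h end in Group 1. The existence of the mismatch does not. Longer treatment in either arm could widen or reverse the difference, by an amount the documents do not allow one to state.

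The primary endpoint is untouched. It would go too far to say that a distorted count would close the trial.

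**What to change.** - **8.2 and the AE-recording entry in Table 1:** record all AEs and SAEs in both arms from randomisation to 96 h after randomisation (the protocol's own 72 h + 24 h), whether or not ICU discharge or End of Study comes first. End earlier only at death, withdrawal or loss to follow-up.
- **By-arm tabulation:** base any between-arm AE table on that window.
- **Group 2:** also record to 24 h after permanent patch discontinuation if that is later, and list those later events separately.
- **4.5:** leave the safety follow-up and its hospital-discharge rule as they are. Only the recording window changes.
- **5.1 and 5.4:** align the end of concomitant-medication recording with the common window. It has the same undefined end in Group 1.
- **4.6:** align the End of Study wording, since ICU discharge may come before 96 h.
- **Terms:** use one defined term in place of *study drug* and *study treatment*.

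The cost is protocol and CRF wording, plus slightly more AE recording in 12 control patients who are already followed to hospital discharge (4.3.2). The downside is that Group 2 events after 96 h have no control comparison. The change should be made prospectively, because AE forms not completed at the time cannot be reliably reconstructed.
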